**Table 5-1 Debio 1347 dose adjustment**

ADVERSE EVENT	GRADE	ACTION
Febrile neutropenia, Neutropenia with infection	4	Permanent discontinuation
	3	Temporary discontinuation until recovery to ≤ Grade 1
Neutropenia	3, 4	Temporary discontinuation until recovery to ≤ Grade 2
Thrombocytopenia	4	Temporary discontinuation until recovery to ≤ Grade 1
	3	If a platelet transfusion is required, temporary discontinuation until recovery to ≤ Grade 1
Diarrhea, constipation, nausea, vomiting, alopecia or skin toxicity	3, 4	Temporary discontinuation until recovery to ≤ Grade 1, but Grade 2 diarrhea manageable with drugs can restart the treatment at 60 mg QD
Hypertension	4	Permanent discontinuation
	3	If uncontrolled, temporary discontinuation until recovery to ≤ Grade 2
Hepatotoxicity (e.g., AST, ALT, ALP increased)	4	Permanent discontinuation
	3	Temporary discontinuation until recovery to ≤ Grade 2
Other non-hematological toxicity (except for alopecia and clinically insignificant electrolyte abnormalities)	4	Permanent discontinuation
	3	Temporary discontinuation until recovery to ≤ Grade 1 or baseline
Hyperphosphatemia		Please refer to treatment guidelines in Appendix E
Recovery from the above AEs		Permanent discontinuation if failure to recover within 21 days, otherwise retreatment at 60 mg QD
Dermatologic toxicities		Please refer to treatment guidelines in Appendix F
Hypercalcemia		Please refer to treatment guidelines in Appendix G

Abbreviations: ALP, alkaline phosphatase; ALT, alanine aminotransferase; AST, aspartate aminotransferase; QD, once daily

In the event a subject requires temporary treatment discontinuation, the Investigator may choose to increase the frequency of the assessments until resolution.

Subjects will be permanently discontinued if a second reduction is necessary. Reduced doses may not be re-escalated. Nevertheless, if according to the Investigator a further increase of the dose to 80 mg daily is expected to improve the clinical benefit of a subject, this increase may be considered after discussion between the Investigator and the Medical Monitor of the study.

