### A. Initial Treatment

Serum phosphorus levels	Intervention
5.5 – 6.9 mg/dL	
Continue treatment with Debio 1347 at current dose AND start on sevelamer oral POWDER 1200mg three times a day (subjects may use tablets if preferred, but tends to have more gastrointestinal toxicity) AND
 
Escalate to sevelamer oral POWDER or tablets 2400mg three times a day if tolerated.
 <hr/> 
Reassess serum phosphorus within 7 days

≥ 7 mg/dL	
Hold treatment with Debio1347
 
Start sevelamer oral POWDER or tablets 2400mg three times a day
 <hr/> 
Add treatment with lanthanum carbonate (Fosrenol®) 1g three times a day
 <hr/> 
Reassess serum phosphorus level within 7 days: If serum phosphorus level < 5.5 mg/dL → resume Debio 1347 at same dose and recheck within 7 days of resumption

	
N.B.
 
 
- Sevelamer should be preferably taken in the mid of meals
 
- Lanthanum carbonate should be taken just after meals
 
- Sevelamer and lanthanum must be administered at least 2 hours after or 4 hours before Debio 1347
 

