A study day between study drug first dose day and last dose day (or last dose at data cut off) is considered a temporary interruption if the number of tablets taken is 0 or missing as recorded in the subject diary eCRF. An episode of temporary interruption is defined as a run of consecutive days with temporary interruption that are flanked before and after by a day with > 0 number of tablets taken. Patients can have multiple episodes of temporary interruption. Temporary interruptions based on the subject diary eCRF will be summarized as follows:

- Number (%) of patients with at least one interruption.
- Number of episodes of interruption per patient presented as continuous and as categories (0, 1, 2, > 2).
- Maximum duration of an interruption episode (days) presented as continuous and as categories (0, ≥ 1 to < 5 , ≥ 5 to < 7 , ≥ 7 to < 14 , ≥ 14 days). This is a summary of the episode with the maximum number of consecutive days with interruption.
- Cumulative duration of interruption days presented as continuous and as categories (0, ≥ 1 to < 5 , ≥ 5 to < 7 , ≥ 7 to < 14 , ≥ 14 days). This is the total interruption days summed over all episodes.

Temporary interruptions due to AE will be defined using the AE CRF data:

- Number (%) of patients with at least one interruption due to AE, defined as having at least 1 TEAE with “Action taken with Study Drug” = Temporarily Interrupted.
- Number of interruptions due to AE per patient presented as continuous and as categories (0, 1, 2, > 2), defined as counting unique start dates of TEAEs with “Action taken with Study Drug” = Temporarily Interrupted. (Note: Counting only unique start dates ensures we do not double-count AEs that are part of the same interruption episode.)

Subject diary information will be presented in a data listing.

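### The SAP counts AE-caused dose interruptions by distinct AE onset dates, which does not prevent double-counting of one hold as its note claims, and which can also merge separate holds

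*SAP*

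**What the plan says.** SAP 10.3.1 Extent of Exposure describes interruptions in two ways.

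- **From the diary, all causes.** A day with zero or missing tablets is an interruption day. An episode is "a run of consecutive days with temporary interruption that are flanked before and after by a day with" tablets taken. The section adds: "Patients can have multiple episodes of temporary interruption".
- **From the AE form, AE-caused.** The number per patient is "defined as counting unique start dates of TEAEs with" the action value Temporarily Interrupted. The accompanying note reads: "Counting only unique start dates ensures we do not double-count AEs that are part of the same interruption episode".

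Both counts are reported as continuous and in the categories 0, 1, 2 and >2. The AE-based section separately gives the number and percentage of patients with at least one AE-caused interruption.

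**The concern.** An AE onset date is not the date on which drug was held. The AE-based rule takes no hold start or stop date and has no link to the diary episodes defined just above it, so its label and its note describe something it does not measure.

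At stake is the only planned count of interruption episodes attributed to AEs. The diary count covers all causes and includes blank diary days. The AE overview in SAP 10.3.2 reports subjects and events, not holds. A reader of the report would take the row as a number of holds, with a written assurance that it is free of double-counting.

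**Working it through.** The plan gives no figure to reproduce, so I applied both SAP 10.3.1 rules as written to made-up patients followed for 112 days. The day numbers are my assumptions; only the rules come from the documents.

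**Rules**
- AE-based count = number of distinct onset dates among flagged TEAEs.
- Diary episodes = number of runs of zero-or-missing-tablet days with a dosing day on each side.

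| Case | Flagged AE onsets | Holds (days) | AE-based count | Diary episodes |
|---|---|---|---|---|
| A: one hold, three AEs, same onset | 20, 20, 20 | 20–27 | 1 | 1 |
| B: one hold, three AEs, different onsets | 17, 19, 20 | 20–27 | 3 | 1 |
| C: one continuing AE record, two holds | 15 | 20–26, 48–54 | 1 | 2 |
| D: two AEs, partial dates imputed to the same day | 1, 1 | 10–14, 20–24 | 1 | 2 |
| E: as C, but a new record opened at worsening | 15, 47 | 20–26, 48–54 | 2 | 2 |

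**Over-count.** Case A is the situation the note has in mind, and there the rule works. Case B is a double-count within one episode (3 − 1 = 2 extra interruptions), which the note says cannot occur.

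**Under-count.** Case C needs an AE that is still open when drug restarts and is then held again. The documents make this possible:
- Protocol Appendix E, step A, at phosphorus of 7 mg/dL or more: "Hold treatment with Debio1347". Once the level is below 5.5 mg/dL: "resume Debio 1347 at same dose and recheck within 7 days of resumption". Step B has a second hold at the same threshold, followed by resumption.
- Protocol 9.1.3 still grades phosphate above ULN but below 5.5 mg/dL as roughly Grade 1. The same hyperphosphatemia AE can therefore be ongoing at restart and run into the second hold.
- Table 5-1 gives another instance of an AE outlasting its hold. For Grade 3 hepatotoxicity the action is "Temporary discontinuation until recovery to ≤ Grade 2". I use this only to show that hold and AE need not end together.

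Case E shows the condition. If the worsening is entered as a new record, the count is right.

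**Merging through imputation.** SAP 8.1.1 sets a missing onset day to the first-dose day when month and year match the first dose and a full AE end date does not precede it; in other months it uses the 1st. Two unrelated AEs can then share an onset date, as in case D.

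**The case against.** The strongest reply is that this is one descriptive row. Protocol 11.5.5 asks only for the incidence of interruptions and reductions, and the proportion with at least one AE interruption answers that for AE causes without error. SAP 10.3.1 also reports dose intensity, compliance, dose reductions and diary episodes with their durations. The listings show AE dates, action taken and diary data, so individual cases can be checked. All of this stands and limits the harm, but none of it makes the note true or supplies the AE-attributed count of holds.

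A reader might draw four stronger conclusions that the documents do not support.

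- *That this is the main measure of tolerability at 80 mg.* Nothing gives it that status. It feeds no endpoint, test, analysis population or stopping decision.
- *That hyperphosphatemia would show 1 instead of 3, with a hold at each of steps A, B and C.* Step B resumes with a dose reduction, step C calls for a reduction, and the text under Table 5-1 requires permanent discontinuation if a second reduction is necessary. A final stop with no later dosing is not a diary episode either. Unless the dose had been re-escalated after discussion with the Medical Monitor, the A-to-B path supports 1 versus 2. Appendix E also describes its content as suggested guidance subject to clinical judgment.
- *That the under-count is certain.* SAP 10.3.2 anticipates repeat records of the same term at different grades, and the documents do not state how sites record a worsening.
- *That a mismatch with the diary count is itself evidence of error.* A correct AE-specific count would also differ from an all-cause count that treats blank diary days as interruptions.

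**Conclusion.** The point holds in a limited form. The note's guarantee is false as written: it is met only when all AEs behind one hold share an onset date. Three different onset dates turn 1 into 3 and move the patient from category 1 to >2. This direction of error follows from the rule alone.

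The under-count, 1 instead of 2, is conditional. It requires either a continuing AE kept as one record across two holds, or separate AEs whose onset dates coincide, for example through imputation.

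The frequency of either error in this trial cannot be estimated, because the documents give no data on AE overlap or on the recording convention. The proportion of patients with at least one AE interruption and every efficacy analysis are unaffected. It is a small defect in a prespecified safety output and cheap to correct.

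**What to change.** Delete the note and replace the rule.

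1. Count distinct diary episodes that contain recorded zero-tablet days, not only missing days, and that begin between the onset and the recorded end date of a TEAE with action Temporarily Interrupted. If that AE is ongoing, the episode must begin on or after its onset. Count each episode once.
2. Use recorded end dates, not imputed ones. SAP 8.1.1 sets a completely missing AE end date to the end of the on-treatment period, which would let one flagged AE absorb every later gap.
3. Show episodes made up only of missing diary days separately.
4. Limit the count to the period with diary data. After Protocol Amendment 2, SAP 10.3 says only AEs, SAEs and AESIs are recorded in the eCRF, so diary entries may stop.
5. Leave the proportion with at least one AE interruption as it is.

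If the link cannot be made reliably, keep the present count, relabel it as the number of distinct onset dates of TEAEs leading to interruption, and still delete the note.

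The cost is a short SAP edit and one date-based merge of two existing datasets; the relabel costs almost nothing. The drawback of the merge is that it depends on diary completeness and infers cause from dates. For some patients it can therefore differ from the AE-based proportion, for example at least one AE interruption but no linked episode. A footnote should say so.

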10.3.2 Adverse Events

Treatment-emergent AE (TEAE) is defined as any AE that either starts or worsens in severity on or after the first administration of the study drug and within 30 days of the last administration of the study drug. Details for handling of completely/partially missing dates are described in Section 8.1.1.

Related TEAE will be defined as any TEAE with “reasonable causal relationship” relationship to study treatment as assessed by the investigator or with missing assessment of the causal relationship. When assessing investigator reported relationship to study drug of the AEs, if an AE reported multiple times changes in causal relationship during an analysis period for a subject, the event is considered related.

When summarizing severity of the AEs, if there are multiple AEs of the same preferred term but different grade, the AE with the maximum CTCAE grade will be reported. If the AE term (SOC and PT) is reported more than once, one of them with missing grade, and at least another with non-missing grade, the maximum CTCAE grade will be chosen from the non-missing grade values and the missing grade can be ignored. If all are of missing grade, then summary of the AE term will include a “missing” category of CTCAE grade.

An overview of adverse events table will be presented for the following AEs overall and includes the number and percentage of subjects and the number of events:

- All TEAE
- TEAE related to study drug
- TEAE with grade 3 or higher
- TEAE with grade 3 or higher related to study drug
- TEAE by worst severity grade according to the NCI-CTCAE v5.0 criteria
- Serious TEAE
- Serious TEAE related to study drug
- TEAE leading to fatal outcome
- TEAE leading to dose reduction
- TEAE leading to temporary treatment interruption
- TEAE leading to permanent treatment discontinuation
- TEAE leading to any dose modification (discontinuation, dose reduction, interruption)
- Treatment emergent adverse event of special interest (AESI – as defined in protocol)
- AESI with grade 3 or higher
- AESI related to the study drug
- AESI with grade 3 or higher related to study drug

The number and percentage of subjects with the following AEs will be summarized using descriptive statistics by SOC and PT. SOC and PTs within each SOC will be displayed in decreasing order of frequency. Subjects who have multiple events in the same PT within a SOC or the same SOC will be counted only once by worst grade (if applicable).

The following by-subject listings will be provided.

- Adverse events
- Serious adverse event

- Adverse events leading to treatment discontinuation
- Adverse events leading to fatal outcome
- AESI
- All deaths and reasons.

These listings will include at least: SOC, PT and reported term, treatment-emergent flag, AE start date/time, AE end date/time, action taken with study medication, relationship, seriousness, CTCAE grade and outcome.

10.3.3 Clinical Laboratory Evaluations

Laboratory parameters include:

- Hematology: Complete blood count with differential, hemoglobin and platelet count.
- Chemistry: Total protein, albumin, indirect and total bilirubin, aspartate aminotransferase, alanine aminotransferase, alkaline phosphatase, electrolytes (sodium, potassium, calcium, and magnesium), serum phosphate, serum creatinine, creatinine clearance, uric acid, bile salts.
- Urinalysis: Red blood cells/hpf, white blood cells/hpf, casts/hpf, protein dipstick test.

For the purposes of summarization in both the tables and listings, all laboratory values will be presented in SI units. Both local and central laboratory values will be included in the analysis.

Hematology and chemistry parameters and corresponding changes from baseline will be presented as descriptive statistics by visit.

Shift tables based on the NCI-CTCAE v5.0 toxicity grading (and ad hoc grading criteria for hyperphosphatemia) will be presented for each hematology and chemistry parameter between baseline and the highest post-baseline NCI-CTCAE v5.0 toxicity grade or the highest post-baseline ad hoc grading criteria for hyperphosphatemia (including unscheduled assessment). The highest toxicity grade can either be above or below the laboratory standard normal range.

For hematology and chemistry parameters without a toxicity grading scale, the shift table will present directional shifts from baseline to above or below the laboratory standard normal range using the maximum increase and/or decrease observed post-baseline. Subjects who experienced both low and high laboratory test results will be reported in a separate “Low and High” column. “Low” and “High” column will represent the subjects having only low/high values respectively.

Boxplots of actual values and change from baseline will be presented by visit for selected hematology and chemistry parameters as relevant. Log transformation will be applied if necessary.

Urinalysis parameters will be summarized by visit using descriptive statistics. For categorical urinalysis parameters, missing data will not be considered as a category and the calculation of frequencies will use the number of non-missing observations. Results from the urinary pregnancy test will be listed.

Summary statistics will be presented for subjects with at least one post-baseline phosphate (phosphorus) level above 5.5:

- Time from start of treatment to Phosphate level of 5.5mg/dL or higher, defined as [earliest date where phosphate \geq 5.5mg/dL] – [date of first administration of the study drug] +1

Category	Parameter	CTCAE Term	CTC Grading direction: Hypo (L)/ Hyper (H)/ No Grading (NA)	CTC Lab Test Unit	CTC Grade 0	CTC Grade 1	CTC Grade 2	CTC Grade 3	CTC Grade 4
Hematology	Hemoglobin	Hemoglobin increased	H	g/L	CHG <= 0	0 < CHG <= 20	20 < CHG <= 40	40 < CHG	
Hematology	Hemoglobin	Anemia	L	g/L	LLN <= aval	100 <= aval < LLN	80 <= aval < 100	aval < 80	
Hematology	Leukocytes	Leukocytosis	H	G/L	aval <= 100			100 < aval	
Hematology	Leukocytes	White blood cell decreased	L	G/L	LLN <= aval	3 <= aval < LLN	2 <= aval < 3	1 <= aval < 2	aval < 1
Hematology	Lymphocytes	Lymphocyte count increased	H	G/L	aval <= 4		4 < aval <= 20	20 < aval	
Hematology	Lymphocytes	Lymphocyte count decreased	L	G/L	LLN <= aval	0.8 <= aval < LLN	0.5 <= aval < 0.8	0.2 <= aval < 0.5	aval < 0.2
Hematology	Neutrophils	Neutrophil count decreased	L	G/L	LLN <= aval	1.5 <= aval < LLN	1 <= aval < 1.5	0.5 <= aval < 1	aval < 0.5
Hematology	Platelets	Platelet count decreased	L	G/L	LLN <= aval	75 <= aval < LLN	50 <= aval < 75	25 <= aval < 50	aval < 25
Hematology	Basophils		NA						
Hematology	Basophils/Leukocytes		NA						
Hematology	Eosinophils		NA						
Hematology	Eosinophils/Leukocytes		NA						

Category	Parameter	CTCAE Term	CTC Grading direction: Hypo (L)/ Hyper (H)/ No Grading (NA)	CTC Lab Test Unit	CTC Grade 0	CTC Grade 1	CTC Grade 2	CTC Grade 3	CTC Grade 4
Hematology	Ery. Mean Corpuscular Hemoglobin		NA						
Hematology	Ery. Mean Corpuscular HGB Concentration		NA						
Hematology	Ery. Mean Corpuscular Volume		NA						
Hematology	Erythrocyte Cell Morphology		NA						
Hematology	Erythrocytes		NA						
Hematology	Hematocrit		NA						
Hematology	Lymphocytes Atypical		NA						
Hematology	Lymphocytes/Leukocytes		NA						
Hematology	Monocytes		NA						
Hematology	Monocytes/Leukocytes		NA						
Hematology	Neutrophils Band Form		NA						

Category	Parameter	CTCAE Term	CTC Grading direction: Hypo (L)/ Hyper (H)/ No Grading (NA)	CTC Lab Test Unit	CTC Grade 0	CTC Grade 1	CTC Grade 2	CTC Grade 3	CTC Grade 4
Hematology	Neutrophils Band Form/Leukocytes		NA						
Hematology	Neutrophils/Leukocytes		NA						
Hematology	Reticulocytes		NA						
Hematology	Reticulocytes/Leukocytes		NA						
Chemistry	Alanine Aminotransferase	Alanine aminotransferase increased	H	U/L	(upcase(bnrind) in ('NORMAL','LOW') and avar <= ULN) or (upcase(bnrind) ='HIGH' and avar <= 1.5*base)	(upcase(bnrind) in ('NORMAL','LOW') and ULN < avar <= 3*ULN) or (upcase(bnrind) ='HIGH' and 1.5*base<avar<=3*base)	(upcase(bnrind) in ('NORMAL','LOW') and 3*ULN < avar <= 5*ULN) or (upcase(bnrind) ='HIGH' and 3*base<avar<= 5*base)	(upcase(bnrind) in ('NORMAL','LOW') and 5*ULN < avar <= 20*ULN) or (upcase(bnrind) ='HIGH' and 5*base<avar<=20*base)	(upcase(bnrind) in ('NORMAL','LOW') and 20*ULN < avar) or (upcase(bnrind) ='HIGH' and 20*base<avar)
Chemistry	Albumin	Hypoalbuminemia	L	g/L	LLN <= avar	30 <= avar < LLN	20 <= avar < 30	avar < 20	

Category	Parameter	CTCAE Term	CTC Grading direction: Hypo (L)/ Hyper (H)/ No Grading (NA)	CTC Lab Test Unit	CTC Grade 0	CTC Grade 1	CTC Grade 2	CTC Grade 3	CTC Grade 4
Chemistry	Alkaline Phosphatase	Alkaline phosphatase increased	H	U/L	(upcase(bnrind) in ('NORMAL','LOW') and aval <= ULN) or (upcase(bnrind) ='HIGH' and aval <= 2*base)	(upcase(bnrind) in ('NORMAL','LOW') and ULN < aval <= 2.5*ULN) or (upcase(bnrind) ='HIGH' and 2*base<aval<=2.5*base)	(upcase(bnrind) in ('NORMAL','LOW') and 2.5*ULN < aval <= 5*ULN) or (upcase(bnrind) ='HIGH' and 2.5*base<aval<= 5*base)	(upcase(bnrind) in ('NORMAL','LOW') and 5*ULN < aval <= 20*ULN) or (upcase(bnrind) ='HIGH' and 5*base<aval<=20*base)	(upcase(bnrind) in ('NORMAL','LOW') and 20*ULN < aval) or (upcase(bnrind) ='HIGH' and 20*base<aval)
Chemistry	Aspartate Aminotransferase	Aspartate aminotransferase increased	H	U/L	(upcase(bnrind) in ('NORMAL','LOW') and aval <= ULN) or (upcase(bnrind) ='HIGH' and aval <= 1.5*base)	(upcase(bnrind) in ('NORMAL','LOW') and ULN < aval <= 3*ULN) or (upcase(bnrind) ='HIGH' and 1.5*base<aval<=3*base)	(upcase(bnrind) in ('NORMAL','LOW') and 3*ULN < aval <= 5*ULN) or (upcase(bnrind) ='HIGH' and 3*base<aval<= 5*base)	(upcase(bnrind) in ('NORMAL','LOW') and 5*ULN < aval <= 20*ULN) or (upcase(bnrind) ='HIGH' and 5*base<aval<=20*base)	(upcase(bnrind) in ('NORMAL','LOW') and 20*ULN < aval) or (upcase(bnrind) ='HIGH' and 20*base<aval)
Chemistry	Calcium Corrected	Hypercalcemia	H	mmol/L	aval <= ULN	ULN < aval <= 2.9	2.9 < aval <= 3.1	3.1 < aval <= 3.4	3.4 < aval
Chemistry	Calcium Corrected	Hypocalcemia	L	mmol/L	LLN <= aval	2 <= aval < LLN	1.75 <= aval < 2	1.5 <= aval < 1.75	aval < 1.5

Category	Parameter	CTCAE Term	CTC Grading direction: Hypo (L)/ Hyper (H)/ No Grading (NA)	CTC Lab Test Unit	CTC Grade 0	CTC Grade 1	CTC Grade 2	CTC Grade 3	CTC Grade 4
Chemistry	Calcium, Ionized	Hypercalcemia	H	mmol/L	aval <= ULN	ULN < aval <= 1.5	1.5 < aval <= 1.6	1.6 < aval <= 1.8	1.8 < aval
Chemistry	Calcium, Ionized	Hypocalcemia	L	mmol/L	LLN <= aval	1 <= aval < LLN	0.9 <= aval < 1	0.8 <= aval < 0.9	aval < 0.8
Chemistry	Creatinine	Creatinine increased	H	umol/L	aval <= ULN	ULN < aval <= 1.5*ULN	(1.5*ULN < aval <= 3*ULN) or (. < 1.5*BASE < aval <= 3*BASE)	(3*ULN < aval <= 6*ULN) or (. < 3*BASE < aval)	6*ULN < aval
Chemistry	Creatinine Clearance	Chronic kidney disease	L	mL/sec	LLN <= aval	1 <= aval < LLN	0.5 <= aval < 1	0.25 <= aval < 0.5	aval < 0.25
Chemistry	Glomerular Filtration Rate	Chronic kidney disease	L	mL/min/1.73m2	LLN <= aval	60 <= aval < LLN	30 <= aval < 60	15 <= aval < 30	aval < 15
Chemistry	Magnesium	Hypermagnesemia	H	mmol/L	aval <= ULN	ULN < aval <= 1.23		1.23 < aval <= 3.3	3.3 < aval
Chemistry	Magnesium	Hypomagnesemia	L	mmol/L	LLN <= aval	0.5 <= aval < LLN	0.4 <= aval < 0.5	0.3 <= aval < 0.4	aval < 0.3
Chemistry	Phosphorus	Hyperphosphatemia	H	mmol/L	aval <= ULN	ULN < aval < 1.78	1.78 <= aval < 2.26	2.26 <= aval < 3.23	aval >= 3.23
Chemistry	Potassium	Hyperkalemia	H	mmol/L	aval <= ULN	ULN < aval <= 5.5	5.5 < aval <= 6	6 < aval <= 7	7 < aval
Chemistry	Potassium	Hypokalemia	L	mmol/L	LLN <= aval	3 <= aval < LLN		2.5 <= aval < 3	aval < 2.5
Chemistry	Sodium	Hyponatremia	H	mmol/L	aval <= ULN	ULN < aval <= 150	150 < aval <= 155	155 < aval <= 160	160 < aval
Chemistry	Sodium	Hyponatremia	L	mmol/L	LLN <= aval	130 <= aval < LLN	125 <= aval < 130	120 <= aval < 125	aval < 120

Category	Parameter	CTCAE Term	CTC Grading direction: Hypo (L)/ Hyper (H)/ No Grading (NA)	CTC Lab Test Unit	CTC Grade 0	CTC Grade 1	CTC Grade 2	CTC Grade 3	CTC Grade 4
Chemistry	Total Bilirubin	Blood bilirubin increased	H	umol/L	(upcase(bnrind) in ('NORMAL','LOW') and aval <= ULN) or (upcase(bnrind) ='HIGH' and aval <= base)	(upcase(bnrind) in ('NORMAL','LOW') and ULN < aval <= 1.5*ULN) or (upcase(bnrind) ='HIGH' and base<aval<=1.5*base)	(upcase(bnrind) in ('NORMAL','LOW') and 1.5*ULN < aval <= 3*ULN) or (upcase(bnrind) ='HIGH' and 1.5*base<aval<= 3*base)	(upcase(bnrind) in ('NORMAL','LOW') and 3*ULN < aval <= 10*ULN) or (upcase(bnrind) ='HIGH' and 3*base<aval<=10*base)	(upcase(bnrind) in ('NORMAL','LOW') and 10*ULN < aval) or (upcase(bnrind) ='HIGH' and 10*base<aval)
Chemistry	Bile Acid		NA						
Chemistry	Calcium		NA						
Chemistry	Creatinine								
Chemistry	Direct Bilirubin		NA						
Chemistry	Indirect Bilirubin		NA						
Chemistry	Protein		NA						
Chemistry	Uric Acid		NA						
Urinalysis	Acid Urate Crystals		NA						
Urinalysis	Amorphous Crystals		NA						
Urinalysis	Bacteria		NA						

Category	Parameter	CTCAE Term	CTC Grading direction: Hypo (L)/ Hyper (H)/ No Grading (NA)	CTC Lab Test Unit	CTC Grade 0	CTC Grade 1	CTC Grade 2	CTC Grade 3	CTC Grade 4
Urinalysis	Calcium Oxalate Crystals		NA						
Urinalysis	Casts		NA						
Urinalysis	Clarity		NA						
Urinalysis	Color		NA						
Urinalysis	Glucose		NA						
Urinalysis	Hyaline Casts		NA						
Urinalysis	Ketones		NA						
Urinalysis	LB Parameter - Urinalysis		NA						
Urinalysis	Leukocyte Cell Clumps		NA						
Urinalysis	Leukocyte Esterase		NA						
Urinalysis	Macroscopic Blood		NA						
Urinalysis	Microscopic Sediment Analysis		NA						
Urinalysis	Mucous Threads		NA						
Urinalysis	Nitrite		NA						
Urinalysis	pH		NA						
Urinalysis	RBC per HPF-CL		NA						

Category	Parameter	CTCAE Term	CTC Grading direction: Hypo (L)/ Hyper (H)/ No Grading (NA)	CTC Lab Test Unit	CTC Grade 0	CTC Grade 1	CTC Grade 2	CTC Grade 3	CTC Grade 4
Urinalysis	Renal Tubular Epithelial Cells		NA						
Urinalysis	Specific Gravity		NA						
Urinalysis	Squamous Epithelial Cells		NA						
Urinalysis	Transitional Epithelial Cells		NA						
Urinalysis	Urine Bilirubin		NA						
Urinalysis	Urine Erythrocytes		NA						
Urinalysis	Urine Leukocytes		NA						
Urinalysis	Urine Protein		NA						
Urinalysis	Urobilinogen		NA						
Urinalysis	WBC per HPF-CL		NA						
Pregnancy test	Choriogonadotropin Beta		NA						

Category	Parameter	CTCAE Term	CTC Grading direction: Hypo (L)/ Hyper (H)/ No Grading (NA)	CTC Lab Test Unit	CTC Grade 0	CTC Grade 1	CTC Grade 2	CTC Grade 3	CTC Grade 4
Pregnancy test	Choriogonadotropin Beta Qualitative		NA						
Pregnancy test	Urine Choriogonadotropin Beta		NA						

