### 9.1.3. Severity of Adverse Events

Adverse events will be graded according to the NCI-CTCAE v5.0 criteria.

Hyperphosphatemia, which is not included in the NCI-CTCAE v5.0, will be graded as follows:

1. Serum phosphate levels > ULN but < 5.5 mg/dL (~ equivalent to Grade 1);
2. Serum phosphate levels 5.5 - 6.9 mg/dL (~ equivalent to Grade 2);
3. Serum phosphate levels 7 - 9.9 mg/dL (~ equivalent to Grade 3, as this is the expected level at which soft tissue calcifications might develop);
4. Serum phosphate levels > 10 mg/dL with or without renal impairment (~ equivalent to Grade 4).

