### C. Subsequent Modifications

Serum phosphorus level	Intervention
> 5.5 mg/dL - 6.9mg/dL	
 
• If not already done, maximize regimen to include:               
 
- Sevelamer oral POWDER or tablets to 2400mg three times a day
 
- Lanthanum carbonate (Fosrenol®) to 1.5g three times a day
 
- Oral acetazolamide 250mg twice a day
 
 
 
• If regimen already maximized, consider dose reduction (without interrupting Debio 1347 assumption)
 
 <hr/> Reassess serum phosphorus level within 7 days
≥ 7 mg/dL	<hr/> Hold treatment with Debio1347 – dose reduction needed <hr/> Maximize regimen to include: 
 
- Sevelamer oral POWDER or tablets to 2400mg three times a day
 
- Lanthanum carbonate (Fosrenol®) to 1.5g three times a day
 
- Oral acetazolamide 250mg twice a day
 
 <hr/> Reassess serum phosphorus level within 7 days: 
 
- If serum phosphorus level < 5.5 mg/dL → resume Debio 1347 with dose reduction
 

	N.B. 
 
- Sevelamer should be preferably taken in the mid of meals
 
- Lanthanum carbonate should be taken just after meals
 
- Sevelamer and lanthanum must be administered at least 2 hours after or 4 hours before Debio 1347
 
- Acetazolamide should be preferably taken just after breakfast and dinner
 

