### D. General Recommendations

1. **In subjects whose serum phosphorus control improves after Debio 1347 dose reduction, de-escalation of the hyperphosphatemia treatment can be considered at the discretion of the Investigator. Subsequent to any such adjustment, serum phosphorus level should be reassessed within 7 days.**
2. **In case of subjects with hepatic or renal impairment, it is recommended not to change hyperphosphatemia treatment even in the case of Debio 1347 dose reduction.**

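### Phosphorus is graded only upward and, because it has a grade, is left out of the Low/High table, so low phosphate appears in no laboratory shift table

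*SAP*

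**What the plan says.** The grading table in SAP section 10.3.3 has a single phosphorus row. Its term, direction, unit and Grade 0 rule read "Hyperphosphatemia H mmol/L aval <= ULN". Grade 1 is "ULN < aval < 1.78", Grade 2 is "1.78 <= aval < 2.26", and Grades 3 and 4 lie above that. The scale comes from protocol section 9.1.3: "Hyperphosphatemia, which is not included in the NCI-CTCAE v5.0, will be graded as follows". The four levels listed there all lie above the upper limit of normal (ULN).

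Section 10.3.3 plans two kinds of shift table:

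- Graded parameters: baseline grade against the highest post-baseline grade, unscheduled samples included. For phosphate this is the ad hoc hyperphosphatemia grade.
- Ungraded parameters: "For hematology and chemistry parameters without a toxicity grading scale, the shift table will present directional shifts", with columns for subjects who were low only, high only, or both.

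The only other phosphate-specific summary in that section is the time to a level of 5.5 mg/dL or more, which also looks upward only.

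Protocol Appendix E sets out stepwise phosphate-lowering treatment with sevelamer, lanthanum carbonate and acetazolamide. At the third step the full regimen includes "Lanthanum carbonate (Fosrenol®) to 1.5g three times a day". For subjects with hepatic or renal impairment, "it is recommended not to change hyperphosphatemia treatment even in the case of Debio 1347 dose reduction". Protocol section 7.7.2.5 also asks for dietary phosphate restriction in all enrolled subjects.

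**The concern.** Hyperphosphatemia was among the most common events in the Phase I study and among those most often severe (protocol section 3.3.2). Phosphate is thus a laboratory value this drug is expected to disturb, and the protocol provides drugs and diet to lower it. A reader of the safety report would want to see both sides: how many subjects went high, and how many fell below the normal range.

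As written, the shift tables can show only the first. A low value meets the Grade 0 rule and so reads as no abnormality. The table designed to separate low from high is closed to phosphorus because it has a hyperphosphatemia scale. At stake is the completeness of a descriptive safety summary. The primary endpoint and the efficacy results are not touched.

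**Working it through.** **1. Reproduce the plan's cut-offs.** Inputs: 5.5, 7 and 10 mg/dL (protocol 9.1.3) and 1.78, 2.26 and 3.23 mmol/L (SAP 10.3.3). Formula: mmol/L = mg/dL × 10 / 30.974. The atomic mass of phosphorus is supplied here, not by the documents.

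| mg/dL | Calculation | mmol/L | SAP |
|---|---|---|---|
| 5.5 | 55 / 30.974 | 1.776 | 1.78 |
| 7.0 | 70 / 30.974 | 2.260 | 2.26 |
| 10.0 | 100 / 30.974 | 3.229 | 3.23 |

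The SAP figures are reproduced. The upper cut-offs are sound; the gap is below the range.

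**2. Apply the phosphorus row to low values.** The documents give no normal limits for phosphate, so ULN was assumed at 1.40, 1.45 and 1.50 mmol/L.

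| Value (mmol/L) | Grade at each assumed ULN |
|---|---|
| 0.2, 0.3, 0.5, 0.7, 0.8 | 0 |
| 1.2 | 0 |
| 1.6 | 1 |
| 1.9 | 2 |
| 2.5 | 3 |
| 3.3 | 4 |

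The choice of ULN makes no difference to the low values, because Grade 0 has no lower bound.

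**3. Follow two illustrative subjects** (ULN 1.45; 0.3 mmol/L taken as below the lower limit of normal, LLN).

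- Baseline 1.1, then 1.3, then 0.3: the post-baseline grades are 0 and 0, so the highest is Grade 0.
- Baseline 1.1, then 1.9, then 0.3: the grades are 2 and 0, so the highest is Grade 2. The 0.3 leaves no trace in the table.

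**4. Check which pattern fits treated subjects.** Appendix E starts sevelamer at 5.5 mg/dL, which is where SAP Grade 2 begins (apart from rounding at exactly that value: 1.776 against 1.78). A subject treated that way on study already has a high grade and follows the second pattern.

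**5. Compare with the other electrolytes.** In the same table, corrected calcium, ionized calcium, magnesium, potassium and sodium each have one row graded upward and one graded downward. Phosphorus has only the upward row. Section 10.3.3 also says that the highest grade may lie on either side of the normal range, but for phosphorus no grade exists below it.

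**6. Check the other outputs.**

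- By-visit statistics show a minimum and quartiles, not numbers of subjects, and SAP 8.4 keeps unscheduled samples and post-dose retests out of them.
- Boxplots are for selected parameters only.
- Listings leave the counting to the reader.
- Adverse event tables do count subjects, but only where the investigator judged the value clinically significant (protocol 9.1.1).

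None gives the number of subjects with any value below LLN.

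**The case against.** The strongest reply has four parts.

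- **One-sided grading is common in this table.** Neutrophils, platelets and albumin are graded only downward; ALT, AST, ALP, bilirubin and creatinine only upward. For phosphorus the SAP simply follows the protocol's scale. This is true and probably explains how the gap arose. It does not close it: every other graded electrolyte has both directions, and phosphate is the one for which the protocol lays out a stepwise lowering regimen.
- **Low phosphate that matters clinically is counted anyway.** Clinically significant laboratory changes are adverse events, and SAP 10.3.2 tabulates these by subject. This stands. What is missing is a count that does not depend on that judgement.
- **The risk is inferred.** No part of the documents names low serum phosphate as a risk. Appendix E calls for reassessment within 7 days at each step, and its general recommendations allow phosphate treatment to be stepped down after a dose reduction if control improves. This also stands and limits the weight of the point.
- **The table shells are in a separate document** not available here. They may already include such a table, but the SAP text does not call for one.

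A reader might go further and infer that subjects made low by phosphate-lowering drugs are reported as Grade 0. The documents do not support that: step 4 shows that most of them would be tabulated at a high grade, with the later low value masked. Nor do the documents report that these drugs cause low phosphate in this study. To say that all affected subjects are missed only restates that the low row is absent; it is not a measured effect.

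**Conclusion.** The point holds as a gap in tabulation. Under SAP 10.3.3 as written, a post-baseline phosphate below LLN appears in no shift table. It is shown either as Grade 0 (subject never above ULN) or not at all behind an earlier high grade. This follows from the wording and does not depend on the assumed ULN.

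Its size in subjects is unknown, because the documents give no frequency of low phosphate. That such values will occur is plausible given the phosphate-lowering regimen and dietary restriction, but it is not documented. Low values are not lost from all output; only a complete subject count is absent. The consequence is confined to descriptive safety reporting in a single-arm study whose enrolment has stopped, so this is a cheap improvement rather than a serious flaw.

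**What to change.** In SAP section 10.3.3, state that phosphorus will also be included in the directional shift table (low only, high only, both) against the laboratory normal range, in addition to the ad hoc hyperphosphatemia grades, and report n (%) of subjects with any post-baseline value below LLN. A split by use of sevelamer, lanthanum carbonate or acetazolamide is optional; SAP 10.3.7 already summarises their use.

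The cost is one sentence and one extra table block. Serum phosphate is already on the chemistry panel, and SAP 10.3 already uses central and local reference ranges for laboratory shifts. No low-phosphate grading cut-offs are needed. Counts may be incomplete after Amendment 2, because SAP 10.3 says that from then on only adverse events, serious adverse events and events of special interest are entered in the eCRF; a footnote should say so. If the SAP is already final, protocol section 11.5.1 allows the table to be described in the report as an additional analysis. Dosing and clinical management are unchanged.
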